7.2.2 Study Days 0-9

Sleep data: Sleep disturbances are common among actively-using opiate and alcohol dependent individuals, severe during the withdrawal phase, and are considered as a long-term risk factor for substance abuse relapse. Chronic insomnia is associated with increased cortisol levels over a 24-hour period. Sleep disturbances and HPA axis activation are expected to be strongly correlated; normalization of HPA axis is predicted to be associated with normal sleep.

The collection of both objective and subjective sleep data and subjective non-sleep activity data will allow an assessment of the validity of the subjective and objective estimates of sleep quality in the effectiveness of suvorexant administration. Sleep data will be collected in 3 ways:

- Objective wrist actigraphy sleep measurements will be collected nightly (Study Nights 0 to 8)
- 2) Subjective sleep and activity data will be obtained the following morning using actigraph logs and EMA survey questionnaires (Study Days 1 to 9). Subjective sleep data will include time to bed, estimated time to fall asleep, night-time awakenings, wake-time in the AM, and quality of sleep.
- 3)
- 4) Standardized measures of sleep quality will be collected. Subjects will complete a modified version of the PSQI at baseline. We will use a modified version of the ISI to measure subjective sleep at baseline (Day 0) and on completion of the study (Day 9) to determine the improvement in sleep quality over the study period.

EMA Daily Diary Data Collection: Ecological momentary assessment (EMA) data refers to the intensive measurement of intra-individual processes in real context (i.e., ecological) and in real

time (i.e., momentary). In the proposed study, such data will be collected via Motorola Droid smart phones that are programmed to elicit the participants' response four times per day, during each of the 9 full study days (Study Days 1 to 9), resulting in approximately 36 assessments per individual. Instructions on how to use the smart phone for the EMA surveys, and what to do if a survey is missed, will be provided verbally on Day 0 to the participant using an approved EMA script. EMA survey administration times will be established to occur at 4 specific time points on a daily basis in order to take advantage of the highly structured patient schedule, maximize compliance, and reduce patient burden. Using the data collection paradigm developed for the National Study of Daily Experiences as a framework (12), EMA surveys will be administered in the morning, early afternoon, late afternoon and evening with minor fluctuations in collection times being adjusted to accommodate specific treatment unit schedules. Research staff will contact the participant using Passport, an in-house simple message system (SMS) used to contact patients while they are at Caron, to remind them to take the EMA surveys. Passport communication does not extend outside of the Caron Treatment Center. EMA reminders will be sent twice daily, at approximately 11 am and 4 pm. If an EMA survey is missed, paper versions of the surveys are provided to the participant to fill out retroactively.

Multiple domains of affect will be drawn from the Extended version of the Positive and Negative Affect Scale and assessed on a daily basis at the four established collection times (PANAS-X; 15). Items included will cover the circumplex spectrum, and include hostility, guilt, sadness, stress, anxiety, fatigue, and happiness. Similarly, formatted items will be used to assess the occurrence and degree of participants craving (16) within each of the 4 EMA surveys. In addition to items inquiring about mood, stress, and craving, the morning assessment will include subjective items related to sleep. These sleep items will record estimated time to fall asleep, night-time wakenings, quality of sleep, daytime sleepiness, and the nightly experience of dreams that involve alcohol/drug content. Two identical and brief mid-day surveys will inquire about mood, stress, and craving to capture aspects of late day experience such as 12 Step meeting attendance and patient perceptions about their day. Thus, our study will be able to capture both the variability in affect/craving and the temporal ordering of stressors and affect necessary to characterize within-day reactivity as well as changes observed in subjective and objective indices of sleep associated with suvorexant administration.

The smart phones that will be used for EMA data collection will have a security application installed that prevents user access to all other applications that are not associated with survey data collection. Smart phones will not be activated on a cellular network resulting in the disabling of voice, text, and internet functions. Research staff will use brief in-person meetings (every other day) as a means to ensure devices are being charged, build rapport, answer participant questions, monitor compliance, and to manually download data for backup storage on the RAs laptop and then uploaded to a secure server, Virtual COLO, at University Park in State College, PA. The server has all of the latest security updates applied as well as the physical security of the data center itself. The only people with access to the server are [name], [name], and [name]. Access to the web-facing application is controlled by CoSign (The standard university login system). Only encrypted communications are used to and from the device, and there is only access to the database through the localhost. The database containing user responses will be backed up periodically (hourly).

Diurnal cortisol: (Study Days 1,2,7,8) Saliva will be collected for cortisol measurement at 5-time points for two consecutive days at two different periods in the study, i.e. 8:00 AM before breakfast, 12:00 PM before lunch, 3:00 PM, 6:00 PM and 9:00 PM. The research staff will visit with the participant at approximately 3 PM (Day 0, 6, 9), 8 AM and 3 PM (Days 1, 2, 7, 8) to

provide fresh cortisol collection kits needed for the next collection and to collect provided saliva samples. Instructions on how to provide saliva samples will be given to the participant on Day 0. Specimens are collected using a cotton swab kit (Salivette, item #51.1534). It has been demonstrated that five samples are adequate to examine circadian variation of cortisol secretion. Cortisol levels will be determined using a commercially-available, high-sensitivity salivary cortisol enzyme immunoassay kit (Catalog # 11-CORHU-E01-SLV; Alpco, Salem, New Hampshire) designed to standardize the measurement of salivary cortisol across research and biomedical laboratories. Saliva cortisol assaying will be done by a certified lab technician in the research laboratory at the Penn State College of Medicine.

7.2.3 Abuse liability: Study Nights 1, 7, and the days following it (Study Days 2 and 8)

Abuse liability will be assessed with a modified protocol which includes the abuse liability battery morning, abuse liability battery night and the observer rated questionnaire. It is based on questions used in previous studies of abuse liability (17). The abuse liability –night battery will be completed by each research participant 30 min after medication administration on study Nights 1 and 7. The abuse liability battery – morning will be completed the morning after drug administration on study Day 2 and 8. The abuse liability battery- morning and night has the same questions related to drug liking, drug value questionnaire, drug effects questionnaire except that there are additional questions asking to categorize the medication effect to one of the seven classed of psychoactive substances on the abuse liability battery-night . The observer rated assessment will be completed by the medication nurse as described below. Our primary measures of abuse liability on the abuse liability battery- morning, night and the observer rated assessment will include the following 5 measures:

- 1. Drug Liking, with questions asking 1) if the drug made them feel high/euphoric, and if they liked the euphoric effect; 2) if the drug made them sleepy, and/or if they liked the sleep effects, or 3) if they disliked the effects of the drug. Each question is scored on a 5-point Likert scale.
- 2. A three-item Drug Value questionnairewill ask participants 1) if they would use the drug to get high; 2) whether they thought that the drug might be addicting; 3) if they would buy the drug illegally to get high.
- 3. The Drug Effect questionnaire, (DEQ) will be used to evaluate how strong a drug effect was felt on a 5-item response scale, ranging from No Drug Effect to Very Strong Effect.
- 4. To further measure abuse liability, patients will also be asked to categorize the drug effect according to one of 7 classes of psychoactive medications. It will be administered on the abuse liability battery morning on the morning of Study Day 2 and 8.
- 5. The Observer-Rated assessment (ORA) will be completed by the medication nurse on the evening of Study Day 1 and 7, 30 min after drug administration.

Abuse Liability Battery Scope (Detailed)

Study Day	1,7	2, 8
Night/Day	Night	Day
Onset/Morn	0	Μ
Measures		
DLQ	Х	Х
DVQ	Х	Х
DEQ	Х	Х
Categorize		Х
O-RA	Х	

O = Onset of Action (30 min after taking medication); M = Morning; DLQ = Drug Liking Questionnaire; DVQ = Drug Value Questionnaire; DEQ = Drug effects questionnaire; Categorize; O-RA = Observer-Rated Assessment

7.2.4 Suvorexant: Study Nights 2-8

Patients will participate in an open 7-day trial of 20 mg suvorexant at night.

7.3 Duration of Participation

Participants will be enrolled in the study for a total of 9 days.

7.4 Test Article(s) (Study Drug(s) and/or Study Device(s))

7.4.1 Description

Subjects will continue on their current off label sleep medication including trazodone, mirtazapine or melatonin for the initial two nights of the study period and then on the study medication, suvorexant for 7 nights.

Trazodone is a sedative triazolopyridine antidepressant, used for the treatment of depression and insomnia because it possesses antidepressant and also anxiolytic and hypnotic activities (18,19). When prescribed as a hypnotic, it is habitually used at low-doses (i.e., 50-150 mg daily at bedtime). The effects of trazodone on sleep have been evaluated in a variety of subjects, including patients with insomnia, depression, substance dependence and normal controls. In general, most studies with Insomnia have shown that trazodone improves subjective and objective sleep. In substance dependent patients, it has shown mixed results, with some studies improving sleep (20,21) and others not in substance dependent subjects (22).

Mirtazepine is an antidepressant used in the treatment of depression and off label for the treatment of Insomnia. It acts by increasing the central noradrenergic and serotonin levels by antagonism of pre synaptic α 2 adrenergic inhibitory auto receptors. Mirtazepine also has potent anti-histaminergic effect at lower doses of 7.5 to 15 mg and hence is used off label for the treatment of insomnia in general population and in substance use disorder subjects (23).

Melatonin is a hormone produced by the pineal gland. Exogenous melatonin is available over the counter in 1 to 20 mg dosage. It is an agonist on melatonin 1, 2 and 3, which improves sleep and stabilizes circadian rhythms. It is found to be efficacious in the treatment of insomnia in the general population (24) but has shown mixed results in the treatment of insomnia in substance use disorders (25).

The sleep medication, suvorexant, has been placed in Schedule IV by the FDA and DEA, and is approved for treatment of Insomnia. The form of the drug will be a 20 mg capsule (1). The drug, to be administered for seven nights under supervision of a nurse, will help determine overall sleep quality, levels of cortisol, and potential abuse liability. The dosage of 20mg was chosen following a recommendation by the lead investigator of the Phase-3 clinical trial for suvorexant performed by Merck. It has been suggested that the difference in side effects between 10 and

20mg is minimal. It has also been suggested that 10mg would have similar effects to a placebo, and that the higher dose of 20mg will be necessary.

7.4.2 Treatment Regimen

During the 9 day study period, subjects will be on their current dosage of medication prescribed by the Caron Foundation physician including trazodone, mirtazapine or melatonin for two nights followed by 7 suvorexant trial. Participants will be administered one 20 mg suvorexant capsule per night for 7 nights. In total, participants will receive 1 capsule per night for a total of 7 nights. There will be no dose adjustments during this trial. All capsules will be taken orally.

7.4.3 Method for Assigning Subject to Treatment Groups

Since this is an open medication trial, there will be no randomization process for assigning treatment to the research subjects stratified by alcohol dependence or opioid dependence.

7.4.4 Subject Compliance Monitoring

Medication compliance will be monitored and documented by the nursing staff at the Caron Foundation during the study. Any compliance issues will be documented and reported to the physician at Caron immediately by the nursing staff at Caron, and [name] will also be notified within 12 hours. A modified abuse liability assessment will also be administered on the evening of Study Night 1 and 7 as well as the following morning (Study Day 2 and 8). On the evening of Study Nights 1 and 7, nursing staff at Caron will complete an observer-rated form 30 minutes after medication administration, to further validate subjective patient reports assessing abuse liability and adverse effects.

7.4.5 Blinding of the Test Article

Not applicable.

7.4.6 Receiving, Storage, Dispensing and Return

7.4.6.1 Receipt of Test Article

The drug capsules will be ordered and received by Synergy Pharmacy, an off-site pharmacy that works with Caron. The Pharmacy will order the medication after receiving a scanned signed informed consent from Caron. The capsules will be ordered in blister packs that contain 7 capsules. These blister packs will be labeled according to FDA and Penn State Pharmacy guidelines.

7.4.6.2 Storage

The storage of the medication will be at the medical detox unit at the Caron Foundation. In this unit is a locked room (nurses station) that contains a locked medication cart, with a locked drawer where the medication will be stored. Therefore, the medication will be double locked. Only 'charge nurses' will have access to the medication. Since the medication does not need to be refrigerated, it will be stored at room temperature in the medication cart. In addition to the study medication, the nurses will also have access to a log containing participant names, in order to observe patient compliance and to perform the appropriate abuse liability questionnaires on the evening of Study Night 1,7. This log will also be kept with the medication in the locked room at the medical detox unit.

7.4.6.3 Preparation and Dispensing

The drug will be ordered by the medical staff at Caron and stored in the medical unit. Caron Foundation nursing staff will administer medication, one capsule per night for 7 nights, and will be overseen by the Foundation's medical staff. As mentioned in section 7.4.6.2, the nursing staff will keep a log of subject names to ensure compliance.

7.4.6.4 Return or Destruction of the Test Article

Final reconciliation of the medication will take place at the Caron Foundation, if appropriate. The Caron Foundation performs these procedures according to DEA regulations. Non-controlled substances are stored in locked medical bins, which are then shipped to a company that will safely destroy the medication. Controlled substances are placed in medical bags where a charcoal-like liquid is added to make the medication 'inactive'. After this procedure, the medication can then be thrown into the trash. Patients who do not complete the entire study will have their medication destroyed via Caron's established medication disposal protocols. Patients will then be redirected to their doctors to discuss any outstanding sleep issues.

7.4.6.5 Prior and Concomitant Therapy

The subjects recruited will be current patients in a residential facility for the treatment of alcohol or opioid dependence. Since the doctors at Caron will be approving patient eligibility, they will know current and past patient medication regimes. Subjects may be taking concomitant medicines/therapies for various reasons at the treatment center. The pharmacy staff at Caron will also know which medications may not be permitted to take with the medication during the study, due to potential counteracting affects. Patients who are concurrently receiving a psychoactive drug for the treatment of an Axis I disorder excluding sedating antidepressants that have been prescribed for the treatment of sleep disturbance, will be excluded, as described in section 3.2.

8.0 Subject Numbers and Statistical Plan

8.1 Number of Subjects

The total sample size will consist of 36 participants stratified by alcohol (n=22) or opioid dependence (n=14). This sample size of convenience is expected to yield 10 evaluable data sets from the opioid group and 15 evaluable data sets from the alcohol group for statistical analysis.

8.2 Sample size determination

The purpose of this pilot study is to determine the feasibility of the study and explore the hypotheses of interest. A sample size of 10 in the opioid group and 15 in the alcohol group will be sufficient to provide meaningful assessment of the study outcomes. The findings from this study will be used to plan a future study.

8.3 Statistical methods

The primary analyses will be mostly descriptive. Summary statistics and graphical methods will be used to examine the distribution of the data. Any potential outliers or leverage points of concern will be evaluated. The outcomes of interest will be summarized and plotted over time for each study group to explore the effect of treatment. Linear or generalized linear mixed effects models will also be used to evaluate the patterns of changes in study outcomes after the treatment of insomnia. Subjects with missing data can be incorporated in the mixed model analysis when data are missing at random. Adverse events and medication compliance will be documented and summarized.

A priori hypotheses derived from the literature as well as from our previous data will be tested separately in alcohol use disorder and opioid use disorder using paired Student's t-tests for pre-post medication contrasts. Specific hypotheses are that both objective measures (sleep actigraphy measures of total sleep time, number of awakenings) and subjective measures of sleep (PSQI, sleep quality) will improve over the course of 10 days on suvorexant. EMA measures of negative mood are expected to decline, and positive moods are expected to increase from baseline to Day 10.

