3.3.2 Follow-up for withdrawn subjects

The primary reason for participant study withdrawal would be due to early discharge from the Caron treatment program prior to successful completion. There would be no follow up with these patients.

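### The a priori hypotheses rest on paired t-tests with no missing-data rule while 11 of 36 data sets are expected to be lost; if only completers are paired, response-related loss can look like benefit

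*Combined protocol and SAP*

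**What the plan says.** Section 8.3 calls the primary analyses mostly descriptive and adds linear or generalized linear mixed models to study patterns of change. For that model it says: "Subjects with missing data can be incorporated in the mixed model analysis when data are missing at random". The a priori hypotheses are handled differently: they "will be tested separately in alcohol use disorder and opioid use disorder using paired" Student's t-tests, comparing before with after medication. No missing-data rule is given for these tests, and section 8.3 does not say which nights or days form the two members of a pair. It describes the mood contrast as running to Day 10, although the schedule in section 7.2 ends on Day 9.

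Section 8.1 plans 22 alcohol and 14 opioid participants, calls this a sample of convenience, and states that it is "expected to yield 10 evaluable data sets from the opioid group and 15 evaluable data sets from the alcohol group for statistical analysis". It does not define an evaluable data set. Section 3.3.2 states: "The primary reason for participant study withdrawal would be due to early discharge from the Caron treatment program prior to successful completion". It continues: "There would be no follow up with these patients".

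**The concern.** A paired t-test uses only subjects who have both members of the pair. If the second member requires completing the study, everyone discharged early leaves the test, along with the actigraphy and EMA data they had already supplied. When those who respond poorly are more likely to leave, the remaining subjects show a better mean change than the group that started treatment. That error favours the hypotheses.

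Selective loss is plausible on the protocol's own account. Section 2.1 ties poor sleep, negative mood and craving to relapse risk, and sections 2.2 and 2.3 report that change in total sleep time tracked later abstinence in the team's previous cohort. Section 8.2 says that the findings will be used to plan a future study, so an inflated change would carry forward into that plan.

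**Working it through.** **Expected loss (section 8.1).** 22 + 14 = 36 enrolled and 15 + 10 = 25 evaluable. Loss overall is 11/36 = 30.6%; alcohol 7/22 = 31.8%; opioid 4/14 = 28.6%. Section 8.1 gives no effect size, SD, power or attrition rate, so the 36 cannot be derived from a formula. The totals are internally consistent.

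**Simulation set-up.** The schedule is from section 7.2: two baseline nights (0 and 1) and seven suvorexant nights (2 to 8). The true mean change is set to zero. Everything else is assumed: night-to-night SD 50 min, between-person SD of change 45 min, and discharge possible after the first suvorexant night, calibrated to 69.4% completing. In the main scenarios, the log-odds of leaving fall by 0.5 or 1.0 for each 60 min of better observed change. As odds, exp(-0.5) = 0.61 is a 39% fall and exp(-1.0) = 0.37 is a 63% fall. Error rates are two-sided against an assumed 5%; section 8.3 states neither alpha nor sidedness.

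**Paired t-test on completers only, no true effect**
- Weaker dependence (39%): mean change about +10 min; error about 7% with 14 enrolled and 10% with 22.
- Stronger dependence (63%): about +17 min; error about 13% with 14 enrolled and 21% with 22.
- Loss following the level of sleep on suvorexant nights, rather than the change: about +6 to +11 min.
- Loss following the level of sleep with baseline nights counted as well: about +2.5 to +4.6 min; error 5% to 6%.
- Loss unrelated to sleep: about zero, with nominal error.

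**Same scenarios, other analyses**
- Mixed model on all available nights: within about 1 min of zero.
- Paired t-test on each subject's mean of available nights: about -1 to -4 min, with near-nominal error.
- Unobserved nights set to the subject's own baseline: +3.8 min (weaker) and +6.5 min (stronger), in the direction of benefit.

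**Wider assumptions.** A second simulation used steeper drop-out (log-odds 1 per 40 min), between-subject SD 40 to 50, individual-response SD 20 to 60 and night SD 40 to 50 min, with 22 enrolled. When loss depended on observed change, completers showed +13 to +25 min and the mixed model -0.7 to -0.1 min. When loss depended on values not observed (the coming night or the latent response), completers showed +7 to +26 min and the mixed model kept +1.5 to +5.0 min. The paired change on available nights stayed between about -5 and +3 min. The mixed model was fitted there with known covariance, so its bias is informative but its error rate is optimistic for groups this small.

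**Which outcomes can gain (sections 7.2 to 7.2.2)**
- Actigraphy (every night) and EMA (four times daily, Days 1 to 9): an early leaver still contributes on-drug data.
- Cortisol (Days 1, 2, 7 and 8): someone who leaves before Day 7 has no on-drug value.
- ISI (Days 0 and 9): someone who leaves before Day 9 has no on-drug value.
- PSQI (baseline only): there is no pair for anyone.

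**The case against.** The strongest reply is that the harm comes from restricting the test to completers, not from using a t-test, and the documents never state that restriction. A paired test needs one pre and one post summary, and the mean of available nights would serve; with it the bias is small. This stands. The wording of section 8.1 and the Day 10 contrast in section 8.3 suggest a completer analysis but do not fix one. The gap is that the evaluable set and the paired values are left open.

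A reader might also infer that nearly a third of subjects will be lost to early discharge because they slept badly. The documents do not support that. Section 3.3.2 gives early discharge as the main reason for withdrawal, not as the cause of all 11 non-evaluable sets. Section 7.2.1 continues eligibility screening after consent, so some losses may be screen failures, and others may be unusable data. Nothing links discharge to response, and the simulated bias shrinks when loss follows overall sleep level.

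A further tempting inference is that the mixed model would avoid the problem. It does so only under missing at random, the condition that section 8.3 itself attaches.

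Finally, this is a pilot with mostly descriptive primary analyses. That lowers the stakes, but section 8.3 still presents these as tests of a priori hypotheses.

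**Conclusion.** The point holds in conditional form. The hypothesis tests have no missing-data rule, 11 of 36 data sets are expected to be lost, and the terms that decide who is tested are undefined. If the evaluable set means completers and loss is related to response on treatment, the expected size is about +6 to +17 min of spurious total sleep time and about 5% to 20% two-sided error against 5%. It is smaller if loss follows overall sleep level and larger under steeper drop-out. All of these sizes rest on assumed SDs, drop-out strengths and alpha. The documents establish neither the mechanism nor the direction of any bias. The mixed model removes the bias under missing at random and otherwise reduces it, and this gain is confined to nightly actigraphy and EMA outcomes.

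**What to change.** In sections 8.1 and 8.3:

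1. Define an evaluable data set and the pre and post values for each outcome, and align the Day 10 wording with the schedule.
2. For actigraphy and EMA outcomes (sleep, mood, craving), make the mixed model already planned the hypothesis analysis, with a generalized linear mixed model for awakenings. Use all available nights or days from every subject with baseline data and at least one suvorexant observation, and let the change on treatment vary between subjects, as in the model checked here.
3. Keep the paired t-test as supportive, computed on each subject's mean of available baseline nights and mean of available suvorexant nights, not on completers only.
4. State that this removes the bias under missing at random and only reduces it otherwise.
5. Report the timing of and reasons for all losses, with baseline values of leavers beside those of completers.
6. Add a delta-adjusted sensitivity analysis that gives early leavers' unobserved nights values worse than the mixed model predicts, over a range of deltas fixed in advance. Do not set those nights to baseline, which itself leans toward benefit.
7. Claim no gain for cortisol, ISI or PSQI. For cortisol and ISI, report how many subjects lack the second assessment.

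The cost is SAP wording and a little programming on data already being collected. The downside is a slightly more model-based analysis in small groups.
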